4.1.7 Storage conditions

Drug supplies will be kept in their original packaging and in a secure limited access storage area according to the recommended (labelled) storage conditions. Where necessary, a temperature log must be maintained to make certain that the drug supplies are stored at the correct temperature. If the storage conditions are found to be outside the specified range, the local clinical monitor (as provided in the list of contacts) is to be immediately contacted.

4.1.8 Drug accountability

pharmacy will deliver the investigational drugs to the investigator upon availability of a valid prescription from the investigator.

The investigator will not order the drugs from the pharmacy before the following requirements are fulfilled:

- Approval of the study protocol by the IRB / ethics committee
- Availability of a signed and dated clinical trial contract between the sponsor and the Head of Trial Centre
- Approval/notification of the regulatory authority, e.g. competent authority
- Availability of a signed and dated clinical trial protocol or immediately imminent signing of the clinical trial protocol
- Availability of licence for clinical research using radioactive isotopes

Only authorised personnel as documented in the form 'Site Delegation Log' may dispense medication to trial subjects. Intake of trial medication during both ambulatory and hospitalized periods must strictly follow the manner specified in the CTP. All unused trial medication must be returned to the sponsor or disposed locally by the trial site upon written authorisation by the clinical monitor. Appropriate retention samples will be kept at until finalization of the clinical trial report. Receipt, usage and return or disposal must be documented on the respective forms. Account must be given for any discrepancies.

4.2 OTHER TREATMENTS, EMERGENCY PROCEDURES, RESTRICTIONS

4.2.1 Other treatments and emergency procedures

There are no special emergency procedures to be followed. No additional treatment is planned. However, in case of adverse events in need of treatment, the investigator can authorise symptomatic therapy. In those cases, subjects will be treated as necessary and, if required, kept under supervision at the trial site or transferred to a hospital until all medical evaluation results have returned to an acceptable level.

4.2.2 Restrictions

4.2.2.1 Restrictions regarding concomitant treatment

No concomitant therapy is allowed. All concomitant or rescue therapies will be recorded (including time of intake on study days) on the appropriate pages of the CRF. Limited amounts of paracetamol are allowed when prescribed by a physician.

In the case of AEs the volunteers will be treated as necessary and kept under constant supervision at the trial centre or transferred to hospital until such time that all the results of the evaluations have returned to a medically acceptable level.

4.2.2.2 Restrictions on diet and life style

While admitted to the trial site the subjects are restricted from consuming any other foods or drinks than those provided by the staff. Standardised meals will be served at the time points

described in the [Flow Chart](#). In addition, subjects are required to refrain from smoking while hospitalized.

On Day 1 and Day 28 starting from 1 hour before drug administration until 2 h after drug intake fluid intake is not allowed except from the 240 mL water administered with the drug intake and an additional 240 mL of water served on Day 1 and Day 28 at 2 h post-dose (mandatory for all subjects). From 2 hours until 22 hours post-dose fluid intake should be within about 1000 to 3000 mL.

On Day 1 and Day 28 subjects will receive a 15 minutes microtracer infusion 1 h after intake of film-coated tablets (i.e., t_{max} for oral dose). The handling instructions will be filed in the ISF.

Poppy-seed containing products should not be consumed starting 2 days before first trial drug administration until last PK sampling of the trial.

For fasting times before drug administration see [Section 4.1.4](#). For fasting times before safety laboratory investigations see [Section 5.2.3](#).

Grapefruits, Seville oranges (sour or bitter oranges) and their juices, and dietary supplements and products including St. John's wort (*Hypericum perforatum*) are not permitted starting 7 days before the first administration of trial medication until after the last PK sample is collected.

Alcoholic beverages are not allowed 48 hours before administration of the compound, before each admission and during the clinic period. During ambulatory phases alcohol consumption is restricted to 24 units a week.

Methylxanthine-containing drinks or foods (such as coffee, tea, cola, energy drinks, and chocolate) are not allowed at days of inhouse confinement.

Subjects should be advised to avoid foods containing a very large amount of tyramine (especially found in fermented food) while taking BI 1467335. These include for example aged cheese, aged meats, soybean products (soy sauce), red wine, tap (draft) beer, St John's Wort, pickled herring, sauerkraut (fermented cabbage), and tryptophan supplements.

Excessive physical activity (such as competitive sport) should be avoided starting 4 days before the first administration of trial medication until the end of trial examination.

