|-------|-------|---|--|--|-------------------|----------------------|--------------------------------------|-------------|----------------------|---|
| 2 | 28 | 660:00 | 20:00 | | | X | | X | X | ↑ ↓ |
| | | 661:00 | 21:00 | | | | X | | | |
| | 29 | 672:00 | 08:00 | | | X | | | | |
| | | 673:00 | 09:00 | | | | X | | | |
| | 30 | 697:00 | 09:00 | | X | | X | X | X | |
| | 32 | 745:00 | 09:00 | Discharge from trial site | | | X | | | |
| 3 | 33-40 | | | End of trial (EOT) examination ^{6, 9} | X | | | X | X | X |

1. Screening includes subject information, informed consent, physical examination, check of vital signs, ECG, safety laboratory (including drug and virus screening), demographics (including determination of body height and weight, BMI, smoking status and alcohol history), relevant medical history, concomitant therapy and review of inclusion/exclusion criteria.
2. The time is approximate; the procedure is to be performed within a time window of 3 h prior to drug administration. After start of treatment, further PK blood sampling (trough level) within 30 minutes before next scheduled dosing.
3. If several actions are indicated at the same time point, the intake of meals will be the last action.
4. Subjects are to be fasted for at least 10 h before sample is taken.
5. Only urine drug and alcohol screening will be done at this time point.
6. End-of-trial (EOT) examination to be performed on Day 34-41, EOT examination includes physical examination, vital signs, ECG, safety laboratory, recording of AEs and concomitant therapies.
7. On Days 3 to 6, 8 to 13, 15 to 20 and 22 to 25, subjects are allowed to take their study medication at home if deemed appropriate by the investigator. Compliance of medication intake will be monitored by subject diary and daily phone contact between subject and site. The scheduled time for drug intake throughout the study is 08:00 (applies for intake at home and at the trial site).
8. Pharmacogenomic sample.
9. For definition of the individual subject's end of trial see [Section 6.2.3](#).
10. Samples for an individual subject beyond 5 h after end of infusion will be only analyzed if for this subject the plasma level of [C-14]BI 1467335 at this time point (i.e., 6:15) is still above LOQ.
11. Subjects will be hospitalized from admission on Day 25 to Day 32.

TABLE OF CONTENTS

| | |
|--|-----------|
| TITLE PAGE | 1 |
| CLINICAL TRIAL PROTOCOL SYNOPSIS | 2 |
| FLOW CHART | 5 |
| TABLE OF CONTENTS | 8 |

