5.2.2.2 Adverse event collection and reporting

AE collection

[figure not shown]
Upon enrolment into a trial, the subject's baseline condition is assessed (for instance, by documentation of medical history/concomitant diagnoses), and relevant changes from baseline are noted subsequently.

Subjects will be required to report spontaneously any AEs as well as the time of onset, end, and intensity of these events. In addition, each subject will be regularly assessed by the medical staff throughout the clinical trial and whenever the investigator deems necessary. As a minimum, subjects will be questioned for AEs (and concomitant therapies) at the time points indicated in the [Flow Chart](#). Assessment will be made using non-specific questions such as 'How do you feel?'. Specific questions will be asked wherever necessary in order to more precisely describe an AE.

A careful written record of all AEs shall be kept by the investigator in charge of the trial. Records of AEs shall include data on the time of onset, end time, and intensity of the event as well as any treatment or action required for the event and its outcome.

The following must be collected and documented on the appropriate CRF(s) by the investigator:

- From signing the informed consent onwards until an individual subject's end of trial:
 - All AEs (serious and non-serious) and all AESIs.
 - The only exception to this rule are AEs (serious and non-serious) and AESIs in Phase I trials in healthy volunteers, when subjects discontinue from the trial due to screening failures prior to administration of any trial medication. In these cases, the subjects' data must be collected at trial site but will not be entered in the CRF or trial database and will not be reported in the CTR.
- After the individual subject's end of trial:
 - The investigator does not need to actively monitor the subject for AEs but should only report related SAEs and related AESIs of which the investigator may become aware of by any means of communication, e.g. phone call. Those AEs should, however, not be reported in the CRF.

The REP for BI 1467335, when measurable drug levels or PD effects are still likely to be present after the last administration, is not known for this clinical trial. Therefore, all AEs reported until the end of trial examination (last per protocol contact) will be considered on treatment (please see [Section 7.3.3](#)).

AE reporting to sponsor and timelines

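### The tyramine advice stops with the last dose, although the protocol says it does not know how long drug levels or effects persist: a minor precautionary mismatch

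*Protocol*

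**What the plan says.** Protocol section 4.2.2.2 sets the advice and its duration in one sentence: "Subjects should be advised to avoid foods containing a very large amount of tyramine (especially found in fermented food) while taking BI 1467335". The examples that follow include aged cheese, aged meats, soy products, red wine, draft beer and St John's wort. Section 11 records that global amendment 1 added prohibited foods to section 4.2.2 to reduce the risk of adverse reactions.

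Section 5.2.2.2 states: "The REP for BI 1467335, when measurable drug levels or PD effects are still likely to be present after the last administration, is not known". The consequence it draws is: "Therefore, all AEs reported until the end of trial examination (last per protocol contact) will be considered on treatment".

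Other limits in section 4.2.2.2 have explicit end points after dosing:

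- Poppy seed: "Poppy-seed containing products should not be consumed starting 2 days before first trial drug administration until last PK sampling of the trial".
- Grapefruit, Seville orange and St John's wort: they "are not permitted starting 7 days before the first administration of trial medication until after the last PK sample is collected".
- Strenuous exercise: to be avoided up to the end-of-trial examination.

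Two provisions limit the practical gap. Flow Chart footnote 11 says: "Subjects will be hospitalized from admission on Day 25 to Day 32". For men in house, section 4.2.2.2 says: "While admitted to the trial site the subjects are restricted from consuming any other foods or drinks than those provided by the staff".

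**The concern.** The sponsor added the food advice for safety and then tied its end to the last dose. The same protocol says it does not know how long the drug or its pharmacodynamic effects last beyond that dose. For counting adverse events, it deals with this uncertainty by carrying the on-treatment period forward to the last planned contact. For a precaution directed at drug effects, it carries nothing forward.

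What is at stake is a small, avoidable exposure of healthy volunteers during a few days at home. Section 4.2.2.2 allows up to 24 units of alcohol a week in ambulatory phases without excluding any type. Once the tyramine advice lapses, therefore, no other visible rule keeps a man at home from the red wine or draft beer on the list. The pharmacokinetic endpoints, the bioavailability analysis and the safety tabulations are not touched.

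**Working it through.** The plan gives no figure to reproduce. The check is day arithmetic from the Flow Chart, plus a comparison of end points.

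**Inputs**

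- Last tablet: Day 28, 648:00 h (Flow Chart). The last infusion starts at 649:00 h.
- Discharge and last PK sample: Day 32, 745:00 h (Flow Chart).
- End-of-trial examination: Days 33 to 40 in the Flow Chart row, Days 34 to 41 in footnote 6. The two do not agree, so both are carried through.

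**Completers**

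- Time in house after the last tablet: 745 − 648 = 97 h (745 − 649 = 96 h from the start of the last infusion).
- From last dose to examination: 33 − 28 = 5 to 40 − 28 = 12 days (row), or 34 − 28 = 6 to 41 − 28 = 13 days (footnote 6).
- Part of that spent at home without the advice: 33 − 32 = 1 to 40 − 32 = 8 days (row), or 34 − 32 = 2 to 41 − 32 = 9 days (footnote 6).

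**End points compared, for completers**

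| Provision | Ends |
|---|---|
| Tyramine advice | last dose, Day 28 |
| Site-controlled food | discharge, Day 32 |
| Poppy seed, grapefruit, St John's wort | last PK sample, Day 32 |
| Exercise limit | end-of-trial examination |
| On-treatment period for adverse events | end-of-trial examination |

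The poppy-seed and grapefruit limits end when in-house cover ends, so they show no practical inconsistency for completers. The relevant comparators are the last two rows. St John's wort is covered to Day 32 by its own rule.

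**Early stoppers**

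Flow Chart footnote 7 allows home dosing: "On Days 3 to 6, 8 to 13, 15 to 20 and 22 to 25, subjects are allowed to take their study medication" at home. A man who stops in one of these stretches may have neither the advice nor site food after his last dose. Section 3.3.4.1 calls for his end-of-trial examination at discontinuation, if possible. An end point defined only by that examination could therefore give him almost no extension. A fixed period is needed for him. The longest planned interval from last dose to examination is 41 − 28 = 13 days.

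**The case against.** The strongest objection is that the deciding evidence is not available. Amendment 1 also changed section 1.2 (drug profile), which is not in the supplied text, and the amendment's rationale cannot be read. A reason for ending the advice with dosing may be given there. The sentence in section 5.2.2.2 sets a window for attributing adverse events and does not mention tyramine. A cautious window for events does not imply that a food interaction lasts as long. The provision is also only advice, about foods with very high tyramine content, and completers have about four days of site-controlled food after the last tablet.

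Most of this stands, and it limits the weight of the point. A reader might infer that men are exposed to a known hazard after dosing, particularly because amendment 1 was marked for immediate implementation to eliminate hazard. The documents do not support that. The marking shows that the sponsor took the risk seriously, but it says nothing about how long the risk lasts. A reader might also infer that completers' diet is uncontrolled from Day 28. It is not, although the protocol does not say that site meals are low in tyramine.

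Nor does the number of doses taken at home measure uncovered time. Doses on Days 2, 7, 14 and 21 are followed by discharge, while home doses on Days 6, 13, 20 and 25 are followed by admission the same day. Men with adverse events needing treatment may be kept under supervision or sent to hospital (sections 4.2.1 and 4.2.2.1), and a man stopping on Days 25 to 28 may still be in house.

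The objection does not supply a reason to end the precaution at the last dose. The protocol calls the period of residual effect unknown, and no visible text extends the advice.

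**Conclusion.** The point holds as a minor one, with medium confidence. The advice stops at the last dose while the protocol calls the residual effect period unknown. The practical gap is 1 to 8 or 2 to 9 days at home for each completer (at most 12 men are planned). For men who stop early while ambulatory, the gap begins at the last dose. Their number cannot be estimated, because the plan gives no dropout rate.

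The risk of a reaction cannot be computed from the visible text, and no interaction after dosing is shown. The conclusion assumes that the unavailable drug profile and subject instructions do not already set an end point; if they do, the point is met. Because the residual period is unknown, no date can be shown to be sufficient. The proposed end point makes the precaution consistent with the rest of the protocol, but does not prove it long enough.

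**What to change.** In section 4.2.2.2, replace the words that tie the tyramine advice to taking the drug with a period from first administration of trial medication to the end-of-trial examination. This matches the exercise limit in the same section and the on-treatment rule in section 5.2.2.2. Add that men who stop early continue the advice for 13 days after their last dose, because their examination may fall at discontinuation. The 13 days come from the visit schedule and are not a washout period. If the drug profile supports a specific period, use that instead. Match the subject instructions, and settle whether the examination falls on Days 33 to 40 or 34 to 41, since it would now end the advice.

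The cost is one amended sentence with its early-stopper clause, the matching line for subjects, and more days of dietary advice at home: up to about 9 for completers (Day 32 to Day 41) and up to 13 for early stoppers. No visit, sample or analysis is added.

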4.3 TREATMENT COMPLIANCE

Compliance will be monitored by either administration of all trial medication in the study centre under supervision of the investigating physician or a designee or during ambulatory period subjects confirm drug intake by phone contact with the study site.

Subjects who are non-compliant (for instance, who do not appear for scheduled visits or violate trial restrictions) may be removed from the trial and the CRF will be completed accordingly (for further procedures, please see [Section 3.3.4.1](#)).

5. VARIABLES AND THEIR ASSESSMENT

5.1 EFFICACY - CLINICAL PHARMACOLOGY

5.1.1 Endpoints of efficacy

No efficacy endpoints will be evaluated in this trial.

5.1.2 Assessment of efficacy

Not applicable.

5.2 SAFETY

5.2.1 Endpoints of safety

Safety and tolerability of the investigational drug will be assessed based on:

- Adverse events (including clinically relevant findings from the physical examination)
- Safety laboratory tests
- 12-lead ECG
- Vital signs (blood pressure, pulse rate)

These parameters will be evaluated in a descriptive way only, and are therefore considered to be 'further parameters of interest'. A confirmatory analysis is not planned (see [Section 7.3](#)).

5.2.2 Assessment of adverse events

5.2.2.1 Definitions of adverse events

Adverse event

An adverse event (AE) is defined as any untoward medical occurrence in a patient or clinical investigation subject administered a medicinal product and which does not necessarily have to have a causal relationship with this treatment.

An AE can therefore be any unfavourable and unintended sign (including an abnormal laboratory finding), symptom, or disease temporally associated with the use of a medicinal product, whether or not considered related to the medicinal product.

Serious adverse event

A serious adverse event (SAE) is defined as any AE which fulfils at least one of the following criteria:

- results in death,
- is life-threatening, which refers to an event in which the patient was at risk of death at the time of the event; it does not refer to an event that hypothetically might have caused death if more severe,

- requires inpatient hospitalisation or
- requires prolongation of existing hospitalisation,
- results in persistent or significant disability or incapacity, or
- is a congenital anomaly/birth defect,
or
- is deemed serious for any other reason if it is an important medical event when based upon appropriate medical judgment which may jeopardise the patient and may require medical or surgical intervention to prevent one of the other outcomes listed in the above definitions.

Examples of such events are intensive treatment in an emergency room or at home for allergic bronchospasm, blood dyscrasias or convulsions that do not result in hospitalisation or development of dependency or abuse.

AEs considered ‘Always Serious’

In accordance with the European Medicines Agency initiative on Important Medical Events, Boehringer Ingelheim has set up a list of further AEs, which by their nature, can always be considered to be ‘serious’ even though they may not have met the criteria of an SAE as defined above.

Cancers of new histology and exacerbations of existing cancer must be classified as a serious event regardless of the duration between discontinuation of the drug and must be reported as described in [5.2.2.2](#), subsections ‘AE collection’ and ‘AE reporting to sponsor and timelines’.

The latest list of ‘Always Serious AEs’ can be found in the RDC system. These events should always be reported as SAEs as described above.

Adverse events of special interest (AESIs)

The term AESI relates to any specific AE that has been identified at the project level as being of particular concern for prospective safety monitoring and safety assessment within this trial, e.g. the potential for AEs based on knowledge from other compounds in the same class. AESIs need to be reported to the sponsor’s Pharmacovigilance Department within the same timeframe that applies to SAE, please see [Section 5.2.2.2](#).

The following are considered as AESIs in this trial:

- Hepatic injury
A hepatic injury is defined by the following alterations of hepatic laboratory parameters:
 - o an elevation of AST and/or ALT ≥ 3 -fold ULN combined with an elevation of total bilirubin ≥ 2 -fold ULN measured in the same blood sample, and/or
 - o aminotransferase (ALT, and/or AST) elevations ≥ 10 fold ULN

These lab findings constitute a hepatic injury alert and the subjects showing these lab abnormalities need to be followed up according to the ‘DILI checklist’ provided in the ISF. In case of clinical symptoms of hepatic injury (icterus, unexplained encephalopathy, unexplained coagulopathy, right upper quadrant abdominal pain,

etc.) without lab results (ALT, AST, total bilirubin) available, the Investigator should make sure these parameters are analysed, if necessary in an unscheduled blood test. Should the results meet the criteria of hepatic injury alert, the procedures described in the DILI checklist should be followed.

Intensity (severity) of AEs

The intensity (severity) of adverse events should be classified and recorded in the (e)CRF according to the Common Terminology Criteria for Adverse Events (CTCAE) Version 4.03 dated 14 June 2010 [[R10-4848](#)] in the (e)CRF.

Causal relationship of AEs

Medical judgment should be used to determine the relationship, considering all relevant factors, including pattern of reaction, temporal relationship, de-challenge or re-challenge, confounding factors such as concomitant medication, concomitant diseases and relevant history.

Arguments that may suggest that there is a reasonable possibility of a causal relationship could be:

- The event is consistent with the known pharmacology of the drug
- The event is known to be caused by or attributed to the drug class.
- A plausible time to onset of the event relative to the time of drug exposure.
- Evidence that the event is reproducible when the drug is re-introduced
- No medically sound alternative aetiologies that could explain the event (e.g. pre-existing or concomitant diseases, or co-medications).
- The event is typically drug-related and infrequent in the general population not exposed to drugs (e.g. Stevens-Johnson syndrome).
- An indication of dose-response (i.e. greater effect size if the dose is increased, smaller effect size if dose is diminished).

Arguments that may suggest that there is no reasonable possibility of a causal relationship could be:

- No plausible time to onset of the event relative to the time of drug exposure is evident (e.g. pre-treatment cases, diagnosis of cancer or chronic disease within days / weeks of drug administration; an allergic reaction weeks after discontinuation of the drug concerned).
- Continuation of the event despite the withdrawal of the medication, taking into account the pharmacological properties of the compound (e.g. after 5 half-lives). Of note, this criterion may not be applicable to events whose time course is prolonged despite removing the original trigger.
- Additional arguments amongst those stated before, like alternative explanation (e.g. situations where other drugs or underlying diseases appear to provide a more likely explanation for the observed event than the drug concerned).
- Disappearance of the event even though the study trial treatment continues or remains unchanged.

